7.9 Primary safety analysis

The primary safety variable is all-cause mortality or unplanned cardiovascular hospitalizations as number of days lost due to unplanned cardiovascular hospitalizations or death between baseline (day of randomization) and 365 days.

The percentage of days lost due to death of any cause or unplanned cardiovascular hospitalizations as the fraction of maximum possible days alive and out of hospital will be analysed by a Wilcoxon signed-rank test comparing both treatment groups. Additionally, the number of days lost due to death of any cause or unplanned cardiovascular hospitalizations will be analysed descriptively by treatment group and in total.

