## 11.4.2 Primary Safety Analysis

The primary safety variable is all-cause mortality or unplanned cardiovascular hospitalizations as days lost due to unplanned cardiovascular hospitalizations or death.

The number of days lost due to death of any cause or unplanned cardiovascular hospitalizations will be analysed by a Wilcoxon signed-rank test comparing both treatment groups. Additionally, the number of days lost due to death of any cause or unplanned cardiovascular hospitalizations will be analysed descriptively by treatment group and in total.

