### 11.5.2 Performance Bias

Potential bias:

Physicians (unblinded) treat patients of the intervention group differently than patients of the control group to reach the aim of the study.

→ Difficult to avoid, the design of the study seems necessary for a realistic study setting. However, the interdisciplinary approach to improve medication adherence is part of the study design. In addition, the CHF medication in both groups will be analysed at V1 and V5.

Contamination at medical practices: physicians intensively engage with the topic (i.e. heart failure, medication adherence and drug-related problems) and apply this additional knowledge to the control patients.

→ Difficult to avoid, the design seems necessary for a realistic study setting. Pharmacists are unaware of the control patients.

Higher detection rate of potential events: Patients in the intervention group receive a more intensive care and have a more intensive contact with health care professionals. The intensified contact could lead to a higher detection rate of events. There is a risk that the recording rate of events differs between control and intervention group.

→ Involvement of e.g. health insurance companies to collect events recorded in the health insurance files.

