5.7 Primary safety variable

The primary safety variable is all-cause mortality or unplanned cardiovascular hospitalizations as days lost due to unplanned cardiovascular hospitalizations or death of any cause between baseline (day of randomization) and 365 days. For death, the remaining days to 365 days will be counted. The days spent in hospital will be added to the days after death until 365 days.

The percentage of days lost due to hospitalisation and death will be calculated as the ratio of the sum of the number of days lost due to death and spent in hospital during the 365-days follow-up and the respective patient follow-up time, expressed in percent.

If a patient terminated the study within 365 days, the days lost between the day of randomization and the day of discontinuation will be analysed accordingly.

For days lost due to unplanned cardiovascular hospitalizations, the admission und discharge day will be counted as one day. Calculations will be done in days.

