7.10.2 Secondary safety analyses

All-cause mortality or unplanned cardiovascular hospitalizations as recurrent event

All-cause mortality or unplanned cardiovascular hospitalizations will be analysed by Negative Binomial Regression with treatment as factor and data from health insurance funds (yes/no) and time within study as offset variable. The logarithm will be used as link function.

Events regarding hospitalization are recorded in the medical practices (eCRF) and will be provided by health insurance funds. However, health insurance data were not available for all patients included in the study. Differences between patients with and without data from health insurance funds cannot be excluded. Therefore, the analysis will be adjusted for data from health insurance funds (yes/no).

The following SAS code can be used:

```
PROC GENMOD DATA=indata;  
    CLASS treatment;  
    MODEL primsafetyendpoint = treatment ... / LINK=log DIST=negbin  
    OFFSET=log_time  
    LSMEANS treatment / DIFF CL;  
RUN;
```

The results are provided showing parameter estimates, LSMEANS and LSMEAN-differences together with their corresponding p-values and 95% confidence intervals as well as the negative binomial dispersion parameter.

Additionally, the number of deaths and unplanned cardiovascular hospitalizations will be analysed descriptively.

Although statistical guidelines (“Points to consider on adjustment for baseline covariates”) suggest adjusting the primary analysis for all stratification variables of the randomization process, this is omitted. It is desired to get a robust result, if one treatment regimen is favourable to the other across all stratification factors.

Several analyses for sensitivity are performed.

1. The analysis is repeated for the PP population
2. The analysis is repeated, but the characteristics from the randomization process are also included in the analysis model (sex (male vs. female), age (<75 vs. ≥75 years), NYHA functional class (I and II vs. III and IV), PHQ-9 score (score <10 vs. ≥10), diabetes mellitus (yes vs. no). All characteristics are included in the model as covariates at the same time without any interaction terms.
3. There is a Kaplan-Meier analysis for the time to first event (death or unplanned cardiovascular hospitalization, whatever occurs first). If no event is reported, time will be censored at the time of last contact. The median time to event will be displayed together with the 25% and the 75% quartile.

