The number of days lost due to death of any cause or unplanned cardiovascular hospitalizations as the fraction of maximum possible days alive and out of hospital will be analysed by a Wilcoxon signed-rank test comparing both treatment groups. Additionally, the number of days lost due to death of any cause or unplanned cardiovascular hospitalizations will be analysed descriptively by treatment group and in total

Percentage of days lost due to hospitalization of any cause or death of any cause

The number of days lost due to hospitalization of any cause or death of any cause as the fraction of actual days alive and out of hospital will be analysed by a two-sided stratified Wilcoxon signed-rank test (van Elteren test) comparing both treatment groups. Additionally, the number of days lost due to hospitalization or death of any cause will be analysed descriptively by treatment group and in total.

The analysis will be adjusted for data from health insurance funds (yes/no).

Unplanned all-cause hospitalizations

The number of unplanned all-cause hospitalizations will be analysed by Negative Binomial Regression with treatment and data from health insurance funds (yes/no) as factor and time within study as offset variable. The logarithm as link function will be used.

Additionally, the number of unplanned all-cause hospitalizations and the cumulative number of unplanned all-cause hospitalizations per visit will be analysed descriptively by treatment group and in total.

There will be a Kaplan-Meier analysis for the time to first unplanned all-cause hospitalization. If no unplanned all-cause hospitalization is reported, time will be censored at the time of last contact or death. The median time to unplanned all-cause hospitalization will be displayed together with the 25% and the 75% quartile.

All-cause mortality

All-cause-mortality (time to death from any cause) will be analysed using the logrank test. The time to death from any cause will be displayed by a Kaplan-Meier curve. The median time to death from any cause will be displayed together with the 95% confidence interval. If no death is reported, time will be censored at the time of last contact. Additionally, the time to death will be analysed descriptively by treatment group and in total.

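### The primary safety test is not stratified by insurer-data availability, although the SAP adjusts closely related hospitalisation analyses for it

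*SAP*

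**What the plan says.** The primary safety variable is days lost to unplanned cardiovascular hospitalisation or "death of any cause between baseline (day of randomization) and 365 days" (SAP 5.7). Protocol 11.4.2 says that it "will be analysed by a Wilcoxon signed-rank test comparing both treatment groups". SAP 7.9 keeps that test, applied to the percentage of days lost: the fraction of "maximum possible days alive and out of hospital will be analysed by a Wilcoxon signed-rank test comparing both treatment groups". Neither section mentions the source of the hospitalisation data.

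SAP 7.10.2 does consider the source. Events come from the practices' case report forms and from insurers, but "health insurance data were not available for all patients included in the study". It continues: "Differences between patients with and without data from health insurance funds cannot be excluded". On that ground it adjusts the negative binomial models for insurer data (yes/no). All-cause days lost "will be analysed by a two-sided stratified Wilcoxon signed-rank test (van Elteren test) comparing both treatment groups", adjusted for the same flag. The cardiovascular days-lost variable over individual follow-up, in the same section, has no adjustment.

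SAP 7.7 plans to calculate under-reporting in patients who have both sources. Protocol 11.5.2 warns: "There is a risk that the recording rate of events differs between control and intervention group". It names insurer data as the remedy.

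**The concern.** Cardiovascular days lost is built from the same hospitalisation records as the analyses that are adjusted, so the SAP's reason for adjusting applies to it equally. No reason is given for leaving it out. The named primary safety variable therefore has less protection than its all-cause secondary counterpart.

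A hospitalisation that no source records cannot be recovered by blinded adjudication. If it was a surviving patient's only one, that patient moves to zero days lost and the rank changes directly. Suppose practices miss some events and one arm has less insurer data. That arm will then appear to lose fewer days. Less insurer data in the intervention arm produces an apparent benefit, and less in the control arm an apparent harm.

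The test is also called signed-rank, which is a paired procedure, while the comparison is between two independent groups. For all-cause days lost the added van Elteren label shows what is meant. SAP 7.9 has no such clarification.

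**Working it through.** **Step 1. The related analyses side by side (SAP 7.9 and 7.10.2).**

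| Analysis | Method | Adjusted for insurer data |
|---|---|---|
| Death or unplanned CV hospitalisation, count | Negative binomial | Yes |
| Unplanned CV, heart failure and all-cause hospitalisations, counts | Negative binomial | Yes |
| All-cause days lost | van Elteren | Yes |
| CV days lost, 365 days (primary safety) | Wilcoxon | No |
| CV days lost, individual follow-up | Wilcoxon | No |

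The Kaplan-Meier analyses are also unadjusted.

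**Step 2. Inputs.** The plan has no size or power figure for this variable to reproduce; Protocol 11.1 powers the study for efficacy only. From the SAP: ITT 110 v 127 (Table 2), and consent withdrawals within 12 months of 6 v 1 (Table 3). SAP 5.4.1 says that insurers provide nothing for patients who withdraw consent. Assumed, because the documents give no values: the share with insurer data, the practices' capture rate without it, full capture with it, 8% deaths, and 30–45% of patients with a CV hospitalisation.

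**Step 3. Apparent ratio of recorded hospitalisation under no true effect.** With share a having insurer data and capture c without it:

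R = [a_I + (1 − a_I)c] / [a_C + (1 − a_C)c]

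- 70% v 70%, any c: R = 1.00.
- 65% v 75%, c = 0.5: 0.825/0.875 = 0.94.
- 60% v 80%, c = 0.5: 0.80/0.90 = 0.89. At c = 0.9: 0.96/0.98 = 0.98.
- 50% v 80%, c = 0.5: 0.75/0.90 = 0.83.

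Exchanging the arms inverts each ratio.

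**Step 4. Rejection rate under no true effect, nominal 5%.** There were 3,000 simulated trials per scenario; the Monte Carlo standard error is √(0.05 × 0.95/3000) = 0.4 points. Ranges span the 30% and 45% hospitalisation assumptions.

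| Insurer data, I v C | Capture without it | Unstratified | van Elteren |
|---|---|---|---|
| 70% v 70% | 50–70% | 4.6–5.0% | 4.6–5.4% |
| 70.0% v 74.4% | 50% | 4.7–5.1% | 3.9–4.8% |
| 65% v 75% | 50% | 5.6–5.7% | 5.3% |
| 60% v 80% | 70% | 5.5–6.6% | 4.9–5.0% |
| 60% v 80% | 50% | 7.0–9.1% | 4.8–5.0% |
| 50% v 80% | 50% | 9.9–14.3% | 5.1–5.3% |

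The second row is close to the one imbalance that the documents show: 6/110 = 5.5% against 1/127 = 0.8% withdrawing.

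A separate set-up used overdispersed hospitalisations (mean 0.5 a year), 8% deaths and availability of 75% v 50%. In 4,000 runs the unstratified test rejected 7.0% at 50% capture, 5.4% at 70% and 5.3% at 85%. Other simulations of the 50% case gave from 6.5% to about 8%.

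**Step 5. Recording that differs by arm, with equal availability.** With share s lacking insurer data, R = [(1 − s) + s·c_I] / [(1 − s) + s·c_C].

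- Capture 85% v 70%: 0.955/0.91 = 1.05 at s = 30%, and 0.925/0.85 = 1.09 at s = 50%. Rejection was 4.7% and 5.9% unstratified, against 4.7% and 5.8% with van Elteren.
- Capture 90% v 40%, s = 30%: 9.6–13.6% unstratified, 9.2–13.8% with van Elteren.

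Stratification does not help in this situation.

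**The case against.** The strongest reply is that the distortion is possible but not shown. It needs a sizeable availability gap between arms together with poor capture by practices, and the documents give neither figure. The withdrawal imbalance alone leaves the test at about 5%. This stands, and it limits the size of the concern.

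The plan also has partial safeguards. The composite of death or unplanned CV hospitalisation is analysed over 365 days as a count with insurer-data adjustment, adjudication is blinded, and under-reporting will be measured. These give an adjusted reading of the same events, but they leave the primary safety test itself unadjusted.

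A reader might infer that stratifying cures the risk named in Protocol 11.5.2. Step 5 shows that it does not. A reader might also take patients with insurer data as fully captured in both arms. The documents do not say so. The practice supplies the referral letter (Protocol 8.2.5), and whether an event known only to the insurer can be adjudicated as unplanned cardiovascular is not stated.

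Finally, insurer-data status is not purely a baseline factor, since later withdrawal of consent removes it, and did so unequally by arm. This qualifies the stratified test slightly and a restricted analysis more.

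**Conclusion.** The omission is certain and runs against the SAP's own reasoning. Its effect is conditional. Under the assumed values, the null rejection rate is about 5% with equal availability, a small gap or capture of about 85%. It is about 6–9% with a 20–25 point gap and 50% capture, and 9.9–14.3% with a 30-point gap.

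A reader might conclude that the primary safety result is biased, or biased towards harm. The documents support neither: they give no availability or capture rates, and the withdrawal imbalance they do show would, if anything, reduce recorded events in the intervention arm. Nor is the 365-day variable shown to be more exposed than its individual-follow-up version, which has the same gap. The change is worth making before the final analysis because it is cheap and would look post hoc afterwards.

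**What to change.** 1. In SAP 7.9, and for CV days lost over individual follow-up in SAP 7.10.2, specify the two-sided van Elteren test: a Wilcoxon rank-sum test stratified by insurer data (yes/no), as already planned for all-cause days lost. Drop the term signed-rank.
2. Add a supportive sensitivity analysis of the primary safety variable and the recurrent-event endpoints, restricted to patients with insurer data. State that complete capture there is an assumption and that withdrawal after randomisation may select the patients.
3. Report insurer-data availability and the SAP 7.7 under-reporting estimate by arm. The general rule at the start of SAP section 7 implies this for all variables, but 7.7 should say it.

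The cost is SAP wording and a few extra runs on data already being collected. In the simulations with equal availability, the stratified test kept close to the 5% level (4.6–5.4%). The restricted analysis is less precise because it uses fewer patients.

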7.10 Secondary analyses

All parameters will be tested for the ITT population on a two-sided level of significance 5%. All p-values will be interpreted in an exploratory way.

All secondary variables will also be analysed for the PP population. These analyses will be considered as exploratory only.

7.10.1 Secondary efficacy analyses

7.10.1.1 Adherence to medication

The primary efficacy analyses will also be repeated for each drug class (ACEi/ARB, BB, MRA), percentage of patients with a mean PDC $\geq 80\%$ (=adherent), and percentage of patients with a PDC $\geq 80\%$ for each drug class (sensitivity analyses for a cutpoint $\geq 88\%$).

We will also perform the different types of calculating the PDC for lipid modifying agents.

We will additionally perform the different types of calculating the PDC between baseline (day of randomization) and 730 days and baseline and individual follow-up time.

7.10.1.2 Quality of life (Minnesota Living with Heart Failure Questionnaire, total score)

The changes to baseline of the total score of the Minnesota Living with Heart Failure Questionnaire after 1 year and, if sufficient data are available, after 2 years will be analysed by an ANCOVA, including treatment as fixed effect and total score at baseline as covariate. Parameter estimates and adjusted mean differences (LSMEAN differences) will be shown together with their corresponding p-values and 95% confidence intervals.

Additionally, the total score as well as the corresponding change to baseline will be analysed descriptively by visit, treatment group and in total.

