STUDY POPULATION	
Inclusion Criteria
 
 
- Age: 60 years and older
 
- Diagnosis of chronic heart failure (CHF)
 
- Stable CHF medication including a diuretic
 
- Hospitalization for decompensated heart failure within past 12 months OR a value of <math>\geq 350</math> pg/mL for BNP or <math>\geq 1400</math> pg/mL for NT-proBNP
 
- Written informed consent
 

	
Exclusion Criteria
 
 
- Regular/assisted use of a weekly dosing aid
 
- Unwillingness or inability to visit a participating pharmacy once a week
 
- Planned cardiac surgery
 
- Life-expectancy < 6 months
 
- Unwillingness or inability to comply with the study protocol (including drug abuse or alcohol dependency)
 
- Participation in other studies (currently or in the last 4 weeks)
 

DURATION OF THE STUDY	The mean follow-up is expected to 24 months with a minimum of 12 months.
NUMBER OF SUBJECTS	
N = 248
 
 
- Estimated effect of intervention: 10% (SD 22%)
 
- <math>\alpha = 0.05</math>, power: 85%
 
- Calculated sample size: 176 + 30% drop out
 

STUDY SITES	
Approximately 40 medical practices
 
Approximately 80 pharmacies

STUDY VISITS	
Intervention and control group:
 
 
- Visits in the medical practice at baseline (V1), after 12 months (V3), and at the end of the study (V6), and, if applicable, after 24 months (V5)
 
- Telephone visits by the medical practice after 6 months (V2) and, if applicable, after 18 months (V4)
 

INTERVENTION	
Regular, pharmacy based intervention conducted in cooperation with the treating physician:
 
 
- Medication review (Type 2a) at baseline: Recording of all medicines currently taken (prescribed medication and self-medication), check for drug-related problems, consolidation of a medication plan considering medication list of treating physician
 
- Regularly (weekly or bi-weekly): Dose-dispensing of the medication (weekly dosing aid), discussion and counselling regarding medication, adherence, potential side effects, and signs and symptoms of cardiac decompensation, blood pressure and pulse measurement, updating medication plan if necessary
 
- If required: Contact with patients' physician
 

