#### 8.2.2 Medical Practice Visits 3 and 5 (V3, V5)

The medical practice records patient characteristics (e.g. vital signs, medical history, and medication) after 12 months (V3) and, if applicable, after 24 months (V5). Furthermore, the patients are asked to fill in questionnaires (table 1).

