5.8.2 Quality of Life (QoL)

Change in MLHFQ -questionnaire overall score between baseline and 365 days (main secondary outcome) and between baseline and 730 days (other secondary outcome). The Minnesota Living with Heart Failure (MLHF) questionnaire will be filled out at screening, visit 3 (after 12 months), and visit 5 (after 24 months). The MLHF is specific for chronic heart failure and consists out of 21 items which are scored on a 6 point Likert-scale (0="not at all" to 5="very much"). Each question is about how much a special facet prevented the patient from living as desired. The total score is calculated as the sum over all non-missing items and ranges from 0 to 105: higher scores indicate worse QoL. A score of < 24 signifies a good, a score between 24 and 45 signifies a moderate, and a score > 45 signifies a poor QoL.

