5.9 Secondary safety variables

The following secondary safety outcomes will be evaluated during 365-days follow-up according to the primary safety variables:

- Percentage of days lost due to unplanned cardiovascular (CV) hospitalizations or all-cause death
- All-cause mortality or unplanned cardiovascular hospitalizations as recurrent event (number)
- Unplanned cardiovascular hospitalizations (recurrent event, number)
- Unplanned hospitalizations for heart failure (recurrent event, number)
- Days lost due to hospitalizations of any cause or death
- Percentage of days lost due to hospitalizations of any cause or death of any cause
- Unplanned all-cause hospitalizations
- All-cause mortality

The following secondary safety outcomes will be evaluated during the patient's individual time within study (=individual follow-up time):

- All-cause mortality or unplanned cardiovascular hospitalizations as recurrent event (number)
- Unplanned cardiovascular hospitalizations (recurrent event, number)
- Unplanned hospitalizations for heart failure (recurrent event, number)
- Percentage of days lost due to unplanned cardiovascular hospitalizations
- Percentage of days lost due to hospitalizations of any cause
- Unplanned all-cause hospitalizations

- All-cause mortality

Table 5 Secondary safety variables - Definition of patients' individual follow-up time

	Intervention group (IG) and control group (CG)
ITT	From randomization until end of study. End of study: 
 - 31.12.2016 - If date of visit 6 or last visit in 2017: 31.12.2016 - If date of final study visit before 30.06.2016: Date of visit 6 - Death: date of death - Withdrawal of informed consent: date of withdrawal - Premature termination of study: date of premature termination

The percentage of days lost due to hospitalisation will be calculated as the ratio of the sum of the number of days lost due to stays in hospital during the respective patient follow-up time and the respective patient follow-up time, expressed in percent.

For days lost due to unplanned cardiovascular hospitalizations, the admission und discharge day will be counted as one day. Calculations will be done in days.

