7.1 Timing of final analysis

When all data from the eCRF, the data processing centres and the health insurance funds will be collected, study data will be prepared for determination of the PDC. Afterwards the final analyses will be performed.

Estimated timing of final analysis: February 2019

All outcomes will be analysed collectively.

7.2 **Patient disposition**

The following patient disposition variables will be presented by numbers and percentages for the total, ITT and the PP population:

- Randomized
- Major protocol violations (with details listed)
- Deaths
- Discontinued except death (with reasons listed)
- Time within the study (≥ 12 months) of the patients who died
- Time within the study (≥ 12 months) of the patients who discontinued except death
- Time within the study of all patients

365 days follow-up

- Terminated prematurely
 - Withdrawal of informed consent
 - Discontinuation
- Death
- Completed first 365 days of study

Follow-up between 365 and 730 days:

- Terminated prematurely
 - Withdrawal of informed consent
 - Discontinuation
- Death
- Study duration < 730 days
- Completed 730 days of study

The following patient disposition variables will be presented by sample characteristics for the total, ITT and the PP population:

- Number of events
- Number of unplanned cardiovascular hospitalizations
- Number of unplanned cardiovascular hospitalizations (365 days)
- Number of events per patient
- Time within the study of the patients who died
- Time within the study who discontinued except death
- Time within study overall
- Time within study of patients who terminated the study regularly

The participation on visit 1, visit 3, and visit 5 as well as the possible reason for drop out will be tabulated for the ITT.

The individual duration of study will be calculated for each patient by duration = (date of end of study – date of randomization) + 1 and will be analysed descriptively.

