7.10.1.4 PHQ-9

The PHQ-9 total score and the changes to baseline will be analysed descriptively by visit (after 1 year and, if sufficient data are available, after 2 years), treatment group and in total. T-tests for comparing treatment groups will be performed.

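### The two-year MLHFQ and PHQ-9 comparisons use observed month-24 scores only; leaving out the month-12 scores and, for PHQ-9, the baseline score costs modest precision

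*SAP*

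**What the plan says.** **Assessment times.** MLHFQ "will be filled out at screening, visit 3 (after 12 months), and visit 5 (after 24 months" (SAP 5.8.2). SAP 5.8.4 gives the same three times for PHQ-9. In the visit tables of both documents, the end-of-study visit V6 is marked for hospitalization only.

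**Who reaches month 24.** The protocol synopsis states: "The mean follow-up is expected to 24 months with a minimum of 12 months". Protocol 8.2.2 places the practice visits "after 12 months (V3) and, if applicable, after 24 months (V5"), so V5 is conditional on still being followed. SAP 7.2 has a disposition line "Study duration < 730 days", without a number. SAP Table 5 closes follow-up at the end of 2016, with earlier ends such as "If date of final study visit before 30.06.2016: Date of visit 6".

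**Rank.** SAP 5.8.2 makes the one-year MLHFQ change the main secondary outcome and lists the two-year change as "between baseline and 730 days (other secondary outcome"). SAP 5.8.4 does the same for PHQ-9. Protocol 6.2 lists both scores at two years without a condition; the synopsis lists PHQ-9 at one year only.

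**Analysis.** For the MLHFQ change, "if sufficient data are available, after 2 years will be analysed by an ANCOVA" (SAP 7.10.1.2), with treatment as fixed effect and baseline score as covariate. PHQ-9 is described after one year and, "if sufficient data are available, after 2 years", and the arms are compared by t-tests (SAP 7.10.1.4). Protocol 11.4.3.2 and 11.4.3.4 name the same methods. SAP 6.1 excludes substitution of missing values. SAP 7.10 makes all secondary p-values exploratory.

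**The concern.** The design itself produces patients who have a month-12 score but no month-24 score. A separate analysis at month 24 drops them from that contrast, although their month-12 score carries information about the missing value. For PHQ-9 the t-test also leaves the recorded baseline score unused as a covariate. Both choices widen the confidence interval for no saving in data collection.

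In addition, the condition of sufficient data has no threshold. As written, whether the two-year comparison is run can be decided after the data are seen, although the protocol lists the outcome unconditionally.

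At stake is the precision and the certain reporting of two exploratory contrasts, not the trial's main conclusion.

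**Working it through.** **1. The plan's own figure.** The only design calculation is for the primary PDC outcome: difference 0.10, SD 0.22, two-sided 5%, power 85% (SAP 1.2). The two-sided t-test needs 87.9, so 88 per arm and N = 176, with power 85.0%. That figure reproduces. It does not bear on this point: no effect, SD or sample size is given for MLHFQ or PHQ-9, and protocol 11.1 says that only the primary efficacy variable is powered.

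**2. Inputs.**
- ITT size: 110 intervention and 127 control, total 237 (SAP 2.2).
- f, the share with a month-24 score: not given. If follow-up were uniform over 12 to 36 months (minimum 12, mean 24), f = (36 − 24)/(36 − 12) = 0.5. The stated minimum and mean do not force this. If 20% averaged 18 months and 80% averaged 25.5 months, the mean is 0.2 × 18 + 0.8 × 25.5 = 24, with f = 0.8.
- r, the month-12/month-24 correlation given baseline: not given; taken as 0.3 to 0.7.
- r0, the baseline/month-24 correlation for PHQ-9: not given; taken as 0.5 to 0.7.

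**3. MLHFQ: joint model against the planned ANCOVA.** Let n patients have a month-12 score and a share f of them a month-24 score. In units of the residual variance given baseline, the observed-case contrast has variance proportional to 1/(fn). The joint model takes the part of month 24 not explained by month 12 from the observed cases, and the explained part from everyone: (1 − r²)/(fn) + r²/n. The ratio is

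(1 − r²) + r²f = 1 − r²(1 − f).

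| f | r | relative variance | variance saved | CI narrower by |
|---|---|---|---|---|
| 0.3 | 0.3 | 0.937 | 6.3% | 3.2% |
| 0.3 | 0.7 | 0.657 | 34.3% | 18.9% |
| 0.5 | 0.3 | 0.955 | 4.5% | 2.3% |
| 0.5 | 0.5 | 0.875 | 12.5% | 6.5% |
| 0.5 | 0.6 | 0.820 | 18.0% | 9.4% |
| 0.5 | 0.7 | 0.755 | 24.5% | 13.1% |
| 0.8 | 0.3 | 0.982 | 1.8% | 0.9% |
| 0.8 | 0.5 | 0.950 | 5.0% | 2.5% |
| 0.8 | 0.7 | 0.902 | 9.8% | 5.0% |

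At f = 0.5, about 118 observed patients (0.5 × 237) would carry the information of about 124, 135, 145 or 157 for r = 0.3, 0.5, 0.6 or 0.7 (118.5 divided by the relative variance). Using all 237 as n is a simplification, since some have no month-12 score; the ratio does not depend on n.

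**4. Simulation check.** With 110 against 127 patients and 4000 runs per setting, the simulated variance savings were 3.8%, 13.6% and 24.8% at f = 0.5 (r = 0.3, 0.5, 0.7; formula 4.5%, 12.5%, 24.5%). At f = 0.8 and r = 0.5 the saving was 4.1% (formula 5.0%). Missingness was independent of outcome, and neither method showed bias.

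**5. PHQ-9: the further factor for baseline.** With equal variances σ² at both times, change has variance 2σ²(1 − r0) and the baseline-adjusted residual has σ²(1 − r0²). The ratio is (1 + r0)/2: 0.75 at r0 = 0.5 and 0.85 at r0 = 0.7. This multiplies the factor in step 3. With r0 = 0.6, r = 0.6 and f = 0.5 it is 0.80 × 0.82 = 0.656. This takes the t-test to be on change; SAP 7.10.1.4 does not say whether the score or its change is tested.

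**The case against.** The strongest reply is that baseline-adjusted ANCOVA at each visit is a valid analysis, protocol and SAP agree on it, and a CI narrower by 2% to 13% (f = 0.5) on an exploratory contrast is close to a matter of taste. The gap is also partly foreseen. SAP 7.2 will tabulate participation at V1, V3 and V5 and the patients with under 730 days, and the scores are described by visit in any case. Month-12 scores are not wasted, since they have their own analysis as the main secondary outcome. All of this stands and limits the weight of the point. It does not touch the unadjusted PHQ-9 test, the unused information at month 24, or the missing threshold.

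Three stronger readings are tempting, and the documents do not support them:

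- **A reader might infer that the gap arises because V6 has no questionnaire.** For a patient who ends before month 24, V6 also falls before month 24. A score there would be a value at a varying earlier time, not the 730-day outcome. The cause is follow-up that ends before V5.
- **A reader might infer that about half the sample is lost.** Neither document gives the share; 0.5 follows only from an assumed symmetric follow-up.
- **A reader might infer that the two-year contrast is biased.** A calendar cut-off is unlikely to depend on a patient's month-12 score. Only dropout after month 12 that is related to that score could bias the observed-case contrast in a way that a model with V3 would reduce, and the documents give no rate for it. SAP Table 3 shows unequal early termination (8 of 110 against 2 of 127), but those patients left before month 12, and a model using V3 would not recover them.

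Nothing suggests, either, that the condition of sufficient data is meant to depend on the result.

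**Conclusion.** The point holds as a modest, avoidable loss of precision. For MLHFQ at month 24 the variance forgone is 4.5% to 24.5% at f = 0.5 and about 2% to 10% at f = 0.8, for r from 0.3 to 0.7. For PHQ-9 the missing baseline adjustment adds a relative variance of 0.75 to 0.85 for r0 of 0.5 to 0.7. f, r and r0 are all assumptions, so the true size cannot be fixed from the documents; if most patients reached V5 it is small.

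The open condition for running the two-year analysis is a separate small defect that needs no assumption.

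Severity is low: the two-year scores rank below the one-year scores, are exploratory, and were not powered.

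**What to change.** **Change.** In SAP 7.10.1.2 and 7.10.1.4, use one repeated-measures model per score: change from baseline at V3 and V5, treatment by visit, baseline score by visit, unstructured covariance. Report the month-12 and month-24 contrasts with 95% CI and the number observed per arm. Replace the condition of sufficient data by always reporting the month-24 contrast with its n. Report deaths by arm alongside. Since protocol 11.4.3.2 and 11.4.3.4 carry the present methods, record the departure.

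**Cost.** No new data are needed, only SAP wording and a standard mixed model in the SAS version already named. Follow-up closed at the end of 2016 under SAP Table 5, so an analytic remedy is the only one left. The month-12 MLHFQ contrast stays essentially the planned ANCOVA. The PHQ-9 t-tests do change, including the one at month 12, which is a main secondary outcome; this should be said openly. The month-24 contrast then rests on a missing-at-random assumption, and for patients who died the model implies a score that does not exist, which is why deaths belong beside it.
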